9.4.5 BASELINE DESCRIPTIVE STATISTICS

Baseline data will be presented by treatment group and total. Data include demographics, complete metabolic panel, complete blood count, HbA1c, TSH, concomitant medications, comorbidities, physical exam measures and baseline values of the outcome measures including the GCSI total score, PAGI-SYM questionnaire subscores and individual severity item scores, GSRS total score, other questionnaires, percent gastric retention at 4-hours, and EGG and satiety results. Means and standard deviations (continuous), medians and inter-quartile range (skewed continuous) or number and percent (binary, categorical) will be reported. P-values will be presented in the footnotes as descriptive statistics only if reaching ≤ 0.05 level and noting that any treatment group differences are due to chance.

Binary and categorical variables will be analyzed using chi-square tests, and continuous variables using t- tests. If a continuous variable is highly skewed, then a nonparametric test (Wilcoxon rank sum tests for comparison of the distribution of changes in each group) will be used to determine significance.

9.4.6 PLANNED INTERIM ANALYSES

There are no planned interim analyses for efficacy or safety. This is a trial with a very short duration of treatment of 4-weeks, that is using a drug that has a history of safety and is non-habit forming. Safety will be monitored by the DSMB throughout the trial.

9.4.7 SUB-GROUP ANALYSES

Post-hoc subgroup analysis of the primary outcome will be done by possible confounders including clinic, etiology (diabetic or idiopathic), gastric retention (delay or not delayed), sex, age (< 50, ≥50 yrs), adherence (80% or more of dose vs <80%), narcotic use at baseline and during trial (vs no use), symptoms at baseline (severe/very severe vs none to moderate), BMI group (normal/underweight vs overweight/obese). If available at the time of the primary paper analyses, then fundic accommodation at baseline (impaired vs normal) will also be included in the subgroup analyses.

Subgroup analyses will use the same models as used for the Intention-To-Treat ANCOVA models for the complete data, as described above. Difference in effects between subgroups will be assessed using the same ANCOVA models augmented with an interaction term for the difference in treatment effects between the subgroups; a P-value less than 0.01 for the interaction term from the augmented ANCOVA will be required for statistical significance of the subgroup difference. If subgroup differences are found, these will be reported and used to provide additional information about the effectiveness of the drug in subgroups of this participant population; however, the primary result of the trial will stand regardless of any subgroup differences that may be found.

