Treatment of side effects: During BESST, if a participant develops non-life threatening side effects that may be attributed to the study drug, the study drug will be stopped only if the participant so desires. If the participant chooses to no longer receive the study drug, the participant will continue to be followed in the trial, in keeping with the intention-to-treat paradigm. In the event of major dermatological reactions such as generalized urticaria, bullous rashes, exfoliative dermatitis, or Stevens-Johnson Syndrome, study drug will be discontinued immediately. Such skin reactions are expected to be infrequent adverse events.

Study visits: This study requires approximately 8 visits to the study center (up to 3 screening visits, randomization visit, and 4 post randomization visits) which may cause some inconvenience to some individuals.

Pregnancy: Since there may be unknown risks to pregnant women and their unborn children, potential participants who are breast feeding, pregnant, or planning to become pregnant will not be allowed to participate in BESST. Participants need to confirm to the best of their knowledge that they are not pregnant and if they become pregnant during the course of the study, they must notify the study investigator immediately and the study drug will be stopped. A urine pregnancy test is obtained at study enrollment and at each visit during study treatment for any females of child-bearing potential to help assure that the participant is not pregnant.

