6.4 STUDY INTERVENTION COMPLIANCE

Assessment of adherence to the assigned study drug will provide clinic staff a means to identify participants having problems with adherence. Adherence will be assessed by:

- Counts of capsules in the participant's returned medication bottle at the end of the trial
- Conducting a brief, structured interview, in which the study coordinator will assist the participants to identify problems in taking the study drug and to estimate adherence to the prescribed medicine since their previous visit during the trial.

These assessments will guide the consideration of strategies to improve adherence and to assess adherence at the end of the trial.

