6.5.1 RESCUE MEDICINE

If symptoms are severe and require further treatment during the trial, participants will be instructed to take rescue medications that they would usually take, such as prochlorperazine or ondansetron for nausea and vomiting, and acetaminophen, ibuprofen, hyoscamine or tramadol for abdominal pain.

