9.3 POPULATIONS FOR ANALYSES

Analysis datasets will include:

- a. Intention-to-Treat – all randomized participants
- b. Safety Analysis Dataset – participants who took at least one dose of treatment
- c. Other Datasets for Sensitivity analyses on a per-protocol basis (as needed: by etiology, sex, race, narcotic use, etc.)
 - i. Complete-Case Analysis Dataset – subset of participants with 4-week outcome data
 - ii. Adherence Analysis Dataset – subset of participants who took at least 80% of treatment

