9.4.2 ANALYSIS OF THE PRIMARY EFFICACY OUTCOME(S)

- Intention-to-Treat (ITT) Analysis Dataset

The primary outcome will be change in the PAGI-SYM questionnaire postprandial fullness/early satiety subscore from baseline to 4 weeks; this subscore is calculated by averaging the scores for 4 PAGI-SYM items: stomach fullness, inability to finish a normal-sized meal, feeling excessively full after meals, and loss of appetite. The subscore average and each item score ranges from 0 (none) to 5 (very severe) on an ordinal scale and is treated as a continuous measure. The treatment effect will be estimated using an intention-to-treat (ITT) analysis of covariance (ANCOVA) model, regressing the change from baseline in postprandial fullness/early satiety subscore at 4-weeks on an indicator variable for treatment group and the baseline value of the outcome. The treatment group difference in adjusted mean change will be presented, along with a two-sided 95% confidence interval, and a P-value.

The confidence limits and P-value will come from the Intention-to-Treat multiple imputation ANCOVA model using all randomized participants, corrected for missing data, as described in [Section 9.2](#) above.

Descriptive analyses will address the assumption of normality of the outcomes using distributional tests (Shapiro-Wilks) and plots (lowess smoothed histograms, boxplots). Tests of normality of the residuals post-ANCOVA regression will be done. If the normality assumptions are not met, then sensitivity analyses using bootstrapped ANCOVA regression will be used to assess validity of the confidence limits and P-values.

Secondary, sensitivity analyses of the primary outcome will use the ITT Dataset and include:

- Complete case ANCOVA, excluding participants with missing data
- The same analysis as above comparing subsets of participants with high vs. not high adherence
- Repeat the Intention-to-Treat analysis adjusting for potential confounders not balanced by the randomization, such as use of narcotics, gastroparesis etiology, percent gastric retention, sex, and age.
- Other secondary, sensitivity analysis conducted will be to model each of the four individual symptom scores of the PAGI-SYM questionnaire postprandial fullness/early satiety subscore using the same methods as above.

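### Adherence and on-trial narcotic use arise after randomisation, so subgroup tests and subsets built on them are biased if their rates or causes differ by arm

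*Combined protocol and SAP*

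**What the plan says.** Section 9.4.7 plans subgroup analyses of the primary outcome by factors that it calls possible confounders. Beside baseline factors such as sex, age and etiology it names "adherence (80% or more of dose vs <80%), narcotic use at baseline and during trial (vs no use". Each factor gets a treatment-by-subgroup interaction test, and "a P-value less than 0.01 for the interaction term from the augmented ANCOVA will be required for statistical significance of the subgroup difference".

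Adherence appears in three other places:

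- Section 9.3 defines an adherence dataset, the "subset of participants who took at least 80% of treatment".
- Section 9.4.1 allows an optional sensitivity analysis in adherent participants.
- Section 9.4.2 lists "The same analysis as above comparing subsets of participants with high vs. not high adherence".

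Section 9.3 also allows sensitivity datasets "as needed: by etiology, sex, race, narcotic use, etc", and 9.4.2 allows adjustment for narcotic use. Neither says whether baseline or on-trial use is meant.

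Both variables are determined after randomisation. Section 6.4 measures adherence from capsules in the "returned medication bottle at the end of the trial" and from interviews. Section 2.3.1 says that, for non-life-threatening side effects that may be attributed to the drug, "the study drug will be stopped only if the participant so desires". Section 6.5.1 allows, for severe symptoms, rescue that includes "hyoscamine or tramadol for abdominal pain"; tramadol is an opioid.

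**The concern.** Randomisation balances the arms over everyone randomised, and within subsets fixed at baseline. It does not balance them within subsets that form during treatment. If people on buspirone stop capsules because of side effects, while people on placebo stop for lack of relief, adherers in the two arms are different kinds of patient. The same holds for participants who stay off narcotics because their symptoms are mild. A strict P threshold limits chance findings but does nothing about this selection.

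What is at stake is interpretation. Section 9.4.7 says that subgroup differences will be reported and used to inform readers about the drug's effectiveness. I found no statement that these particular sets lose the protection of randomisation, and no causal method for adherence.

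**Working it through.** **Inputs from the plan.** Section 9.2: 54 per arm, two-sided 0.05, target difference 0.5 points, SD 0.8, SD of change 1.0, baseline to week-4 correlation 0.55. Section 9.4.7: interaction threshold 0.01. The documents give no non-adherence rates and no link between adherence and symptoms, so those are assumed below. The true effect on the subscore is zero throughout, and no data are missing. Effects are buspirone minus placebo; higher scores are worse.

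**Step 1: the plan's sample size.** SD of change = 0.8 × √(2 × (1 − 0.55)) = 0.759. At 90% power for 0.5 points this needs 49 per arm; 49 × 1.1 = 53.9, so 54 per arm and 108 in total. This matches the plan and sets the simulated trial size.

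**Step 2: closed form for the bias.** Let s be the ANCOVA residual SD, p the non-adherence rate, z the normal cut-off for p, φ(z) the normal density there, and g the correlation between the tendency not to adhere and the week-4 residual. The mean residual is −g·s·φ(z)/(1 − p) in adherers and +g·s·φ(z)/p in non-adherers. Taking s from the SD of change 1.0 with equal variances at both visits, s = √(1 − 0.55²)/√(2 × 0.45) = 0.88. With g = 0.5, g·s = 0.44. Rejection rates are from 4,000 simulated trials per case.

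- *Same rate and reasons (20%, g = 0.5 in both arms).* The terms cancel. Adherent-only P<0.05 in 5.0%; interaction P<0.01 in 0.8%.
- *Only rates differ (10% placebo, 40% buspirone, g = 0.5 in both).* Placebo adherers: −0.44 × 0.1755/0.90 = −0.086. Buspirone adherers: −0.44 × 0.3863/0.60 = −0.283. Difference −0.20, which is 0.20/0.5 = 40% of the target difference. Adherent-only P<0.05 in 18.6%; interaction P<0.01 in 0.9%. With a weaker tie to outcome the bias in adherers is about −0.08.
- *Reasons differ (20% each, g = 0.5 on placebo, 0 on buspirone).* Adherers: +0.44 × 0.2800/0.80 = +0.154. Non-adherers: −0.44 × 0.2800/0.20 = −0.616. Adherent-only P<0.05 in 13.0%; interaction P<0.01 in 22.2%.

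Using SD 0.8 instead, s = 0.8 × √(1 − 0.55²) = 0.668 and the biases in points shrink in proportion (0.668/0.88 = 0.76). The rejection rates do not depend on s.

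**Step 3: vary the strength of the link.** Here non-adherence follows the change seen at week 2: 20% in each arm, random on buspirone, SD 0.8, correlations 0.6 (baseline to week 2, assumed), 0.7 (week 2 to week 4, assumed) and 0.55 (plan). There were 3,000 trials per row.

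| Placebo link to week-2 change | Interaction P<0.01 | Adherent-only P<0.05 |
|---|---|---|
| 1.0 | 24% | 14% |
| 0.7 | 9.9% | 8.9% |
| 0.5 | 4.7% | 7.4% |
| 0.3 | 1.5% | 5.7% |
| 0.5 in both arms | 0.9% | 5.4% |

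At the complete link the bias is about +0.12 points in adherers and about −0.5 in non-adherers.

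**Step 4: the wording of 9.4.2.** Comparing high with not-high adherence can be read as a direct comparison of adherers with non-adherers. In the first case of Step 2, where nothing differs by arm, that comparison still shows 0.77 points, with P<0.05 in 97% of trials. It measures who adheres, not what the drug does.

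**Step 5: the remedy.** The intention-to-treat contrast rejects in 4.4% to 5.5% of trials across the Step 2 family of scenarios, with bias of at most 0.01 points. On-trial narcotic use was not simulated; the argument there is structural.

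**The case against.** The plan contains real safeguards. Section 9.4.1 rests the primary conclusion on intention-to-treat and makes the adherent-only analysis optional. Section 9.3 offers its extra datasets only as needed. Section 9.4.7 calls its subgroups post-hoc and says that the primary result stands whatever they show. All of this holds, and it limits the point to supportive analyses.

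The size is also open to challenge. A reader might infer that the interaction test misleads in about a quarter of null trials. That needs placebo non-adherence to be wholly determined by week-2 response and buspirone non-adherence to be wholly random, and the documents support neither. With a weak link the rate is close to nominal.

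A reader might also infer that an entirely inert drug would produce these findings. It would not: if side effects, adherence and rescue use are alike in both arms, the between-arm contrasts keep their nominal error.

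Nor does the bias always flatter buspirone. In the week-2 scenario it makes the drug look worse in adherers and better in non-adherers, while higher non-adherence on buspirone alone makes it look better in adherers.

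What remains is that post-hoc and sensitivity labels do not restore comparability. The plan itself gives routes by which assignment could affect both variables.

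**Conclusion.** The point holds conditionally. These comparisons are biased, with no effect on the symptom score, when non-adherence or on-trial narcotic use is tied to symptoms and its rate or causes differ by arm.

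- If reasons differ as in Step 3, the 0.01 interaction test rejects in about 1.5% to 24% of null trials and the adherent-only test at 0.05 in about 6% to 14%.
- If only rates differ, the interaction test stays near nominal but the adherent-only contrast is biased, by about −0.08 to −0.20 points at 10% versus 40%.
- If neither differs, both tests are nominal.

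These ranges rest on assumed rates and links. The documents do not support reading this as a threat to the primary conclusion, or as an objection to narcotic use at baseline, which is a valid subgroup factor. It is worth correcting because the change is cheap and the plan intends to use subgroup differences as information on effectiveness.

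**What to change.** - **Section 9.4.7:** delete adherence as a subgroup factor and restrict narcotic use to use at baseline.
- **Sections 9.3 and 9.4.2:** state that narcotic-use datasets and adjustment refer to baseline use only.
- **Sections 9.3, 9.4.1 and 9.4.2:** label any retained adherence-subset result as not protected by randomisation and not evidence of effectiveness. Say in 9.4.2 exactly which contrast is meant.
- **Reporting:** present adherence and on-trial narcotic use by arm as descriptive outcomes.

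A complier-average estimate with randomised arm as instrument is optional. If used, it should state its exclusion restriction, which is doubtful at an 80% cut because participants below it still receive drug.

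The cost is SAP wording and the loss of the adherence and on-trial narcotic subgroup tests. The sample size and the primary analysis do not change.

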9.4.8 TABULATION OF INDIVIDUAL PARTICIPANT DATA

For monitoring of adverse effects, individual data may be presented to the Data and Safety Monitoring Board. In that case, study participants will be identified only by study IDs. Names and other unique individual identifiers such as Social Security Number are not collected by the study and therefore will not be presented to the DSMB. Individual data including ID will not be presented in a manuscript.

9.4.9 EXPLORATORY ANALYSES

Outcomes for exploratory or ancillary analysis, depending on the timeframe of additional work required to interpret and quality control data from the gastric emptying scintigraphy tests and the electrogastrogram test digital scans at the GpCRC central resource centers, are listed below:

The first and second outcomes are ancillary:

1. Changes at 4-weeks in Fundic Accommodation (FA) using digital analyses of the GES test images
2. Changes and mean changes, respectively, at 4-weeks in EGG test gastric rhythm measures and water satiety: a) clinical EGG diagnosis (normal, tachygastria, bradygastria, mixed gastric dysrhythmias; b) percentage time and distribution of power in normal 3 cpm EGG activity before and after the water load satiety test and c) total volume of water ingested.

This following outcome is exploratory since it is using the PRO daily-diary version of the ANMS GCSI questionnaire that is not currently validated; however, these outcomes may provide sensitivity analyses on several secondary outcomes.

3. Mean changes at 4-weeks in each of the 7 items on the ANMS GCSI-DD questionnaire: nausea, postprandial fullness, early satiety, upper abdominal pain, episodes of vomiting, episodes of retching, overall symptom severity, as well as the total core symptom composite score. The average severity scores from the last 7-days of treatment are subtracted from the 7-day average baseline severity scores for each of the items.

These two outcomes listed below are ancillary since they are not necessarily powered to detect a change between treatment groups; however, they may provide information on buspirone to develop further hypotheses in the future.

4. Changes at 4-weeks in each of the 15 symptom severity items measured on the PAGI-SYM instrument not included in secondary outcomes item 3, including retching, lower abdominal pain, lower abdominal discomfort, constipation, and diarrhea
5. Changes at 4-weeks in each of the 5 subscores of the Gastrointestinal Symptom Rating Scale (GSRS).

10 SUPPORTING DOCUMENTATION AND OPERATIONAL CONSIDERATIONS

10.1 REGULATORY, ETHICAL, AND STUDY OVERSIGHT CONSIDERATIONS

10.1.1 INFORMED CONSENT PROCESS

Template consents will be prepared for the GpCRC BESST Trial by the SDRC. Individual clinical centers may add material, but may not delete material thought to be necessary for informed consent. Clinical centers may reformat and reword information to conform to their local IRB requirements. A consent form must be signed by each participant. The consent form will describe the purpose of the study, the procedures to be followed, and the risks and benefits of participation. A copy of the consent form will be given to the participant and this fact will be documented in the subject's study files.

10.1.1.1 CONSENT AND OTHER INFORMATIONAL DOCUMENTS PROVIDED TO PARTICIPANTS

Consent forms describing in detail the study intervention, study procedures, and risks are given to the participant and written documentation of informed consent is required prior to starting intervention and administration of the study intervention and procedures. The following consent materials, BESST Combined Consent – HIPPA Adult, are submitted to IRBs with this BESST protocol.

10.1.1.2 CONSENT PROCEDURES AND DOCUMENTATION

Informed consent is a process that is initiated prior to the individual's agreeing to participate in the study and continues throughout the individual's study participation. Consent forms will be Institutional Review Board (IRB)-approved and the participant will be asked to read and review the document. The investigator will first explain the research study to the participant and answer any questions that may arise. A verbal explanation will be provided in terms suited to the participant's comprehension of the purposes, procedures, and potential risks of the study and of their rights as research participants.

Participants will have the opportunity to carefully review the written consent form and ask questions prior to signing. The participants should have the opportunity to discuss the study with their family or surrogates or think about it prior to agreeing to participate. The participant will sign the informed consent document prior to any procedures being done specifically for the BESST study. Participants must be informed that participation is voluntary and that they may withdraw from the study at any time, without prejudice. A copy of the informed

consent document will be given to the participants for their records. The informed consent process will be conducted and documented in the source documents (including the date) for the participant, and the form signed before the participant undergoes any study-specific procedures. The rights and welfare of the potential participants will be protected by emphasizing to them that the quality of their medical care will not be adversely affected if they decline to participate in this study.

To minimize in-person contact time between the participant and staff during the Covid-19 pandemic and as permitted by the site-specific IRB and/or the sIRB, participants will be offered a telephone or virtual review of the consent in place of the in-person review of the consent. Signature of the consent will take place in person at the study visit and after confirmation that all of the participant's questions about the study have been answered.

10.1.2 STUDY DISCONTINUATION AND CLOSURE

This study may be temporarily suspended or prematurely terminated if there is sufficient reasonable cause. Written notification, documenting the reason for study suspension or termination, will be provided by the suspending or terminating party to study participants, investigators, funding agency, the Investigational New Drug (IND) sponsor (N/A) and regulatory authorities. If the study is prematurely terminated or suspended, the Principal Investigator (PI) will promptly inform study participants, the Institutional Review Board (IRB), and sponsor and will provide the reason(s) for the termination or suspension. Study participants will be contacted, as applicable, and be informed of changes to study visit schedule.

Circumstances that may warrant termination or suspension include, but are not limited to:

- Determination of unexpected, significant, or unacceptable risk to participants
- Demonstration of efficacy that would warrant stopping
- Insufficient compliance to protocol requirements
- Data that are not sufficiently complete and/or evaluable

Study may resume once concerns about safety, protocol compliance, and data quality are addressed, and satisfy the DSMB, sponsor, IRB and/or Food and Drug Administration (FDA).

